## 2 CHANGES TO PROTOCOL PLANNED ANALYSES

A summary of adverse events by maximum intensity was planned in protocol Section 9.4.4. This was removed per AZD7442 program-level data presentation decision.

Enrolment into the study has been discontinued due to FDA feedback. No participant has been included for Cohort 3, and the full analysis set will contain 46 instead of 100 participants. Planned analyses for Cohorts with no participants will not be conducted.

## 3 DATA ANALYSIS CONSIDERATIONS

### 3.1 Timing of Analyses

#### 3.1.1 Interim Analysis

At least one interim analysis is planned to be conducted in this study after a minimum of 12 adolescent participants, age  $\geq 12$  to  $< 18$  years old, complete the Day 92 study visit.

Additional interim analyses may be conducted to support regulatory requirements. No adjustment will be made for multiple hypotheses testing.

Please see Section [5 Interim Analysis](#) for details on the analysis content.

### **3.1.2 Data Safety Monitoring Board**

An independent DSMB will provide oversight to ensure safe and ethical conduct of the study. The DSMB will regularly meet and make any necessary recommendations to the Sponsor based on their evaluations of emerging data. In particular, the DSMB will conduct a safety evaluation once 14 days of safety data are available for 6 participants or more. Subsequent DSMB meetings will review safety data after 21, 36, 51, 66, 81 and 96 participants have been dosed with AZD7442. Data summaries will be prepared and provided to the DSMB.

Details for the DSMB and summaries to be prepared will be outlined in a DSMB Charter and a DSMB analysis plan.

## **3.2 Analysis Populations**

The study population of pediatric participants aged  $\geq 29$  weeks gestational age to  $< 18$  years are split into three cohorts by their COVID-19 status at study entry and dosed considering weight categories.

### **Cohorts**

Cohort 1: Pediatric participants who are SARS-CoV-2 negative at baseline

Cohort 2: Pediatric participants who are SARS-CoV-2 positive at baseline and have mild to moderate COVID-19

Cohort 3: Pediatric participants who are SARS-CoV-2 positive at baseline and have severe COVID-19

In case a participant is assigned to Cohort 1 via a negative rapid COVID-19 test at screening, but the confirmatory test result is positive, the participant stays assigned to Cohort 1.

Cohort 3 will be empty due to discontinuation of enrolment. No change to enrolment in Cohort 1 and 2 was made.

### **Route of IMP administration**

IM: Participants will receive a single dose of AZD7442 given via IM (AZD8895 followed by AZD1061 administered separately)

IV: Participants will receive a single IV infusion (AZD8895 and AZD1061 co-administered) based on the participant's body weight

### **Age groups**

The participants' ages will be categorized into the following categories using age information captured during the randomization procedure.

1.  $\geq 12$  years to  $< 18$  years
2.  $\geq 6$  years to  $< 12$  years
3.  $\geq 1$  years to  $< 6$  years
4.  $\geq 29$  week gestational age to  $< 1$  year
  - a.  $\geq 1$  month to  $< 1$  year
  - b.  $\geq 29$  week gestational age to  $< 1$  month

### **Weight categories**

1.  $\geq 1.5$  to  $< 5$  kg
2.  $\geq 5$  to  $< 15$  kg
3.  $\geq 15$  to  $< 40$  kg
4.  $\geq 40$  kg

## **3.3 General Considerations**

### **3.3.1 General Study Level Definitions**

All original and derived parameters as well as demographic and disposition data will be listed and described using summary statistics. All safety data (scheduled and unscheduled) will be presented in the data listings.

Summaries will be based on the visit schedule, but unscheduled and repeated assessments captured will be used for definition of baseline or for identification of worst post-baseline evaluations. If there is an unscheduled and a scheduled assessment with the same date, the unscheduled assessment will be assumed to be a repetition and the scheduled result used for summaries.

Frequency counts (number of participants [n] and percentages) will be produced for each qualitative variable. Descriptive statistics (n, mean, SD, median, minimum and maximum) will be calculated for each quantitative variable (unless otherwise stated). Descriptive statistics will only be presented if  $n > 3$ . If no participants have data at a given time point,  $n = 0$  will be presented. If  $n < 3$ , only the n, minimum and maximum will be presented, and if  $n = 3$ , only the n, median, minimum and maximum will be presented; the other descriptive statistics will be left blank.

The CI to a geometric mean will be determined by log-transforming the observations, calculating the 95% confidence limits to the arithmetic mean of the transformed data and back-transforming the confidence limits with the exponential function.

Percentages will be presented to one decimal place. Percentages will not be presented for zero counts. Percentages will be calculated using n as the denominator. The denominator should be clearly presented in each table.

Rounding should be the last operation in the treatment of data. There should be no rounding of intermediate results during the calculation of any derived value. Zeros at the end of a number should be retained.

All statistical analyses and production of tables, figures, and listings will be performed using SAS® version 9.4 or higher. All other requirements and specifications for programming and presentation of TFLs will be specified in the TFL shells document.

### **3.3.2 Baseline**

Unless otherwise specified, baseline is defined as the last non-missing measurement taken prior to the dose of IMP. These can be assessments from screening, Visit 1 or unscheduled or repeated assessments prior to IMP administration.

### **3.3.3 Change from Baseline**

Change from baseline will be defined as the value post-dosing minus the baseline defined, for each timepoint.

Percent change from baseline will be calculated as:

$$\text{Percent change from baseline} = ([\text{visit value} - \text{baseline value}]/\text{baseline value}) \times 100$$

### **3.3.4 Study Day**

Study Day 1 is defined as the date of first dose of IMP.

For visits (or events) that occur on or after first dose of study treatment, study day is defined as (date of visit [event] – date of first dose of study treatment + 1). For visits (or events) that occur prior to first dose, study day is defined as (date of visit [event] – date of first dose of IMP). There is no study day 0 defined for this study.

### **3.3.5 Handling of Missing Data**

In general, other than the below there will be no imputation of missing data unless explicitly stated.

In case of missing data in collection of AE start date or start time, that is not reported as unknown:

- AEs with start date/time at the time of or after dosing (for each specific treatment/dose) until Follow-Up Visit will be assigned to the specific treatment/dose.
- AEs with completely unknown start dates will be imputed with the date and time of dosing, unless the end date is known and prior to dosing; in that case the start date will be imputed as the date of Screening and a time of 00:00.
- AEs with unknown start times, but with start date known, will be imputed with a time of 00:00, unless the start date corresponds to the dosing date. In this case the start time will be imputed with the time of dosing. If this results in a start date/time after end date/time of the AE, then the time will also be imputed with 00:00.
- Missing day: impute with the 1st of the month, unless the month and year in which the AE started is a month and year in which IMP was administered, then the day will be imputed with the first day on which IMP was administered in that month. If this results in a start date after the end date, then the day will be imputed with the first day of the month.
- Missing month: impute with the 1st month in which IMP was administered. If this results in a start date after the end date of the AE, then the month will be imputed with JAN. If the known year part is not a year in which IMP was administered, then the month will also be imputed with JAN.
- Missing day and month: impute with the day and month of dosing. If this results in a start date after end date, then the day and month will be imputed with 01JAN. If the year is not a year in which IMP was administered, then the day and month will also be imputed with 01JAN.
- Missing year: impute with the year of dosing
- Missing times will be imputed as 00:00 h or with the time of dosing for events starting on a dosing day.

When imputing a start date, care should be taken to ensure the start date is sensible, ie, prior to the end date.

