8.3.1 Time Period and Frequency for Collecting AE and SAE Information

Adverse events will be collected from the time of IMP administration throughout the study, up to and including the last visit. After IMP administration on Day 1, participants will be monitored on site for a minimum of one hour for general safety, including injection/infusion site reactions and hypersensitivity reactions (including anaphylaxis).

Serious adverse events will be recorded from the time of signing of the ICF throughout the study, up to and including the last visit.

If the Investigator becomes aware of an SAE with a suspected causal relationship to the IMP that occurs after the end of the clinical study in a participant treated by him or her, the Investigator shall, without undue delay, report the SAE to the Sponsor.

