#### 4.2.2.1 Adverse Events

Adverse Events will be collected throughout the study from date of informed consent until the end of the follow-up. The MedDRA will be used to code the AEs using the latest available version.

Treatment-emergent AEs are those AEs with onset date/time at or after dosing.

A listing will cover details for each individual AE including MedDRA SOC, PT, reported term, seriousness, start and stop date/time, relatedness to IMP, intensity (mild, moderate, severe and CTCAE grade 1-5), actions taken, time from last dose, whether or not leading to withdrawal from the study, AESI identification and outcome.

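### Two SAP rules for partial adverse event start dates have no floor at dosing, so a true post-dose event can be dated before dosing and leave the TEAE and AESI summaries

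*SAP*

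**What the plan says.** SAP 3.3.5 treats each pattern of missing date parts separately.

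- Year missing: "Missing year: impute with the year of dosing". No exception follows.
- Month missing: "Missing month: impute with the 1st month in which IMP was administered". The reported day is kept. There is a fallback, "If this results in a start date after the end date of the AE, then the month will be imputed with JAN", and January is also used when the known year is not a dosing year.
- Day missing, with month and year equal to those of dosing: "then the day will be imputed with the first day on which IMP was administered in that month".
- Day and month missing: "Missing day and month: impute with the day and month of dosing", when the known year is the dosing year.
- Date completely unknown: the dosing date and time, unless a known end date precedes dosing.

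The general safeguard at the end of the section is that "care should be taken to ensure the start date is sensible, ie, prior to the end date". Nothing compares an imputed start with dosing.

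SAP 4.2.2.1 then defines status by date: "Treatment-emergent AEs are those AEs with onset date/time at or after dosing". The same section lists AESIs as a subset of TEAEs, and TEAE and AESI incidence are among the main safety summaries. Protocol 4.1 follows each participant to Day 366.

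**The concern.** A follow-up of one year crosses into the next calendar year for every dosing date except 1 January, where it reaches only the anniversary. Assigning the dosing year to an event that happened after New Year therefore moves it back a full year. Assigning the dosing month while keeping the day moves an event before dosing whenever its day number is smaller than the dosing day. The end-date check cannot catch either error, because the imputed start is earlier than the true one.

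The neighbouring rules default to dosing when the date parts leave the order open. An AE with a completely unknown date is thus kept as treatment-emergent, while one with a known day and month may not be. That looks like an oversight. At stake is the derivation behind a primary safety summary: for true post-dose events these two rules can only remove TEAEs, never add them.

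**Working it through.** The plan states no figure on this point, so there is none to reproduce. The rules were applied as written to every dosing date in a 365-day year and every true onset from 0 to 365 days after the dose.

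**Inputs from the documents:** the rules in SAP 3.3.5; the TEAE definition in SAP 4.2.2.1; follow-up to Day 366 with a Visit 6 window of ±15 days; and screening from Day -7 (protocol 1.3 and 4.1).

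**Assumptions not in the documents:** dosing dates and onsets are uniform; each AE lasts 7 days with a known end date; a day number that does not exist in the imputed month becomes the last day of that month.

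**Two examples, dose on 15 October 2022**
- True onset 10 March 2023, end 20 March 2023, year missing: imputed 10 March 2022, seven months before dosing.
- True onset 5 November 2022, end 12 November 2022, month missing: imputed 5 October 2022, ten days before dosing.

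Both pass the end-date check. Neither is a TEAE.

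**Year missing.** Let k be the number of days from 1 January to the dosing date (0 to 364). Of the 366 possible onset dates, k lie between the next 1 January and the day before the anniversary, and each is moved to before dosing. The anniversary itself lands on the dosing date. The misdated share is k/366.

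| Dosing date | k | k/366 |
|---|---|---|
| 1 January | 0 | 0% |
| 1 April | 90 | 24.6% |
| 1 July | 181 | 49.5% |
| 15 October | 287 | 78.4% |
| 31 December | 364 | 99.5% |

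The mean of k is 182, so the average share is 182/366 = 49.7%. With follow-up to the end of the Visit 6 window (day 380 after the dose) the enumeration gives 47.9%. All misdated records pass the end-date check. Those placed more than 7 days before dosing number k − 7 when k exceeds 7. Summed over dosing dates this is 63,903 of 365 × 366 = 133,590, or 47.8% of all onsets.

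**Month missing.** If the known year is the one after dosing, January of that year is used and the date stays post-dose. If it is the dosing year, the date is wrong when the onset falls in a later month on a smaller day number. For a 15 October dose, 365 − 287 = 78 onsets fall in the dosing year. Of these, 14 in November and 14 in December are misdated: 28/78 = 35.9%. A dose on the first of a month gives 0%. Over all dosing dates the share is 43.8% of onsets in the dosing calendar year. Half of all onsets fall in that year (mean 183 of 366), so the overall share is 0.438 × 0.50 = 21.9%.

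**Comparison.** The missing-day rule and the missing-day-and-month rule both give 0% in the same enumeration. So do the two rules above once a floor at dosing is added.

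**The case against.** The best answer is that the affected records will hardly exist. Participants are contacted weekly and asked about the past 7 days (footnotes to protocol Tables 2 and 3), so a site can normally place an event in its month and year. Data are quality-checked (protocol Appendix A 7) and cleaned before an interim cut (SAP 5). A start date months before dosing would also be visible in the AE listing. All this bears on frequency and stands, but none of it changes the written rule, which a program would apply to whatever partial dates remain.

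Several stronger readings are tempting, and the documents do not support them.

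- *The AE start-date rules as a whole are faulty.* Only two patterns are affected; the other partial-date rules gave no misdating.
- *About half of AESIs with a partial date would be lost.* The 50% is for missing-year records under uniform onset. Protocol 4.2.1 expects infusion, hypersensitivity and injection-site reactions within minutes to hours, and for those the dosing year and month will almost always be right.
- *A pre-dose date is impossible for a non-serious AE.* Protocol 8.3.1 says "Adverse events will be collected from the time of IMP administration throughout the study", but SAP 4.2.2.1 starts collection at informed consent. Until these are reconciled, a pre-dose non-serious AE cannot be ruled out.
- *The primary safety counts in general lose events.* The SAE definition does not use TEAE status, and every AE is listed. Only the TEAE and AESI summaries are exposed.
- *Each lost event costs 1/46 = 2.2 percentage points.* The tables are split by cohort and route, so 46 is not their denominator. A child also leaves the any-TEAE row only if that child has no other TEAE.

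The error is not strictly one-directional either. A late-December screening SAE with its year missing and dosing in January could be moved to after dosing, although the end-date check may catch it.

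**Conclusion.** The point holds, narrowly. As written, SAP 3.3.5 can date a true post-dose AE before dosing in two cases: (i) year missing with day and month known; (ii) month missing with day known and the year equal to the dosing year. Such an event loses TEAE status, and AESI status where that applies.

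Among records with these patterns, the misdated share is about 50% for (i). For a missing month it is about 22% overall, or 44% when the onset is in the dosing calendar year. These shares rest on uniform dosing and onset dates. The number of such records is not given and is probably very low, so the expected effect on the tables is small. The reason to act is that a stated rule for a primary safety derivation gives a wrong answer and is easy to correct.

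**What to change.** Amend SAP 3.3.5 as follows.

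1. Year missing, day and month known: use the first year that puts that day and month on or after dosing and not after any known end date.
2. Any partial date: if the imputed start falls before dosing, and the recorded date parts do not themselves show a pre-dose onset, set the start to the date and time of dosing, unless a known end date is before dosing. Worded this way, the floor also covers ongoing AEs with no end date.
3. Leave unchanged any SAE recorded in the eCRF as starting before dosing.

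Separately, reconcile the start of AE collection in protocol 8.3.1 with SAP 4.2.2.1.

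The cost is a few lines in the SAP and a small change to the derivation program. There is one small downside: a genuine screening-period event with a partial date that continues past dosing may be counted as treatment-emergent. That is conservative for safety and matches how the neighbouring rules already behave.

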### **3.3.6 Visit Window**

Scheduled visits will be analysed as captured in the electronic case report forms. Early discontinuation visits will be mapped to the chronologically closest not-performed visit.

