Procedure	Treatment and follow-up period							Early discontinuation visit	For details, see section:
	Visit 1	Visit 2	Visit 2A	Visit 3	Visit 4	Visit 5	Visit 6		
Day	1	4, 8, 11 or 15^a	8	31	92	183	366		
Window (days)	NA	± 2	± 3	+ 5	± 5	± 10	± 15		
Targeted physical examination		X		X	X	X	X	X	8.2.1
Vital signs (including pulse oximetry)	X ^b (post dose)	X		X	X	X	X	X	8.2.2
TriPLICATE 12-lead ECG							X	X	8.2.3
Serum chemistry, hematology				X		X	X	X	8.2.4
Coagulation tests				X	X		X	X	8.2.4
Urinalysis ^c				X	X	X	X	X	8.2.4
Pregnancy test – urine (females of childbearing potential only) ^d	X (pre-dose)								8.2.4
Concomitant medications	X	X		X	X	X	X	X	6.5
Verify eligibility criteria	X								5.1, 5.2
IMP administration	X								
Sample for SARS-CoV-2 RT-PCR (central laboratory) ^e	X ^{f, g} (pre-dose)		X ^g						8.6.1
Serum sample for SARS-CoV-2 serology (anti-nucleocapsid) (Cohort 1 only)				X	X	X	X	X	8.5.3.2

Table 3 Schedule of Activities: Treatment and Follow-up Period for Participants Other Than Neonates – Main Study

Procedure	Treatment and follow-up period							Early discontinuation visit	For details, see section:
	Visit 1	Visit 2	Visit 2A	Visit 3	Visit 4	Visit 5	Visit 6		
Day	1	4, 8, 11 or 15 ^a	8	31	92	183	366		
Window (days)	NA	± 2	± 3	+ 5	± 5	± 10	± 15		
Pharmacokinetics, pharmacodynamics, and ADA assessments									
Serum sample for AZD7442 PK assessment	Only participants receiving AZD7442 IV (post dose ^b)	X		X	X	X	X	X	8.5.2
Serum sample for AZD7442 ADA assessment	X (pre-dose)			X	X	X	X	X	8.5.3.1
Serum sample for SARS-CoV-2 nAbs assessment	X (pre-dose)			X	X	X	X	X	8.5.4.1
Nasal sample for exploratory PK assessment		X		X	X	X	X	X	8.5.2.2
Safety assessments									
Post dose observation – 1 hour ⁱ	X								8.3.1
AEs ^j	↔							X	8.3
SAEs, MAAEs, and AESIs ^j	↔							X	8.3

^a Participants will be randomly assigned to have a PK sample taken on one of the following days: Day 4, 8, 11, or 15 (ie, one sample per participant). See Section 6.3 for information.

^b Perform 15 minutes (± 5 minutes) after the IMP injection is complete.

^c Collection of urine samples from participants who are unable to provide urine samples is not mandatory provided that a reasonable attempt has been made to collect the samples.

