8.5.2 Pharmacokinetics

- Serum samples will be collected for measurement of serum concentrations of AZD7442 (AZD8895 and AZD1061) at either Day 4, 8, 11, or 15 (one sample) and Days 31, 92, 183, and 366 (one sample on each day), as specified in the SoA (Section 1.3). For participants who receive AZD7442 via an IV infusion, a serum sample should also be taken at the end of the infusion on Day 1 from the opposite side of the body. Serum samples should still be taken even if the participant is outside the visit window specified in the SoA.
- Samples may be collected at additional time points during the study if warranted and agreed upon between the Investigator and the Sponsor, eg, for safety reasons. The timing of sampling may be altered during the course of the study based on newly available data (eg, to obtain data closer to the time of peak or trough matrix concentrations) to ensure appropriate monitoring.
- Serum samples will be used to assess the PK of AZD7442 following IM and IV administration. Samples collected for analyses of AZD7442 serum concentration may also be used to evaluate safety or efficacy aspects related to concerns arising during or after the study.
- Samples will be collected, labeled, stored, and shipped, as detailed in the Laboratory Manual.
- AZD7442 PK parameters (eg, maximum serum concentration, AUC), if data permit, will be calculated based on AZD7442 serum concentrations following IM and IV administration.

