### **3.3.7.2 For Pharmacokinetic Analysis**

In case a serum PK sample is drawn at an unscheduled visit, PK analysis will include the unscheduled concentrations.

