#### **4.1.3 Protocol Deviations**

##### **4.1.3.1 Definitions and Derivations**

Important deviations from the protocol (IPDs) may lead to the exclusion of participants or data from the PKS or SES. Deviations will be assessed and classified during the study and finalized before database lock. IPDs include those deviations from the protocol that are likely to have an impact on the perceived safety of study treatments or outcome assessment.

IPDs will include the following at a minimum:

- Violation of key inclusion and/or exclusion criteria.
- Administration of prohibited concomitant medications that are expected to influence the outcome of this study.
- Deviations from planned dose or administration procedure of the IMP.
- Relevant time window deviations expected to influence key safety and/or PK assessments.

All important protocol deviations will be listed. A qualitative summary table will be provided.

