##### 4.2.1.1 Serum Concentration Data

For AZD7442 mAbs, the serum concentrations for each scheduled time point will be summarized based on the PKS.

A listing of all serum concentration-time data, ie, PK scheduled times, actual sample collection times, sample actual relative times (ie, relative to time of administration of the IMP), as well as derived sampling time deviations (ie, difference between actual and scheduled time) will be presented for all participants in the SAF.

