##### 4.2.1.2 Figures for Serum Concentration Data

Individual serum concentration-time data (AZD7442, AZD8895 and AZD1061) will be graphically presented on linear and semi-logarithmic scales, for all participants in the PKS. Combined individual serum concentration versus actual times will be plotted on both the linear and semi-logarithmic scales for all participants in the PKS. Plots will be grouped by cohort, route of administration and weight categories. Figures for the gmean ( $\pm$ gSD) serum concentration-time data will be presented by cohort, route of administration and weight categories (1, 2, 3, 4 and all) on both a linear and semi-logarithmic scale (no gSD presented for the semi-logarithmic scale), for all participants in the PKS.

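### SAP 3.3.6 can place a leaver's serum PK concentration at a much later nominal day in by-visit tables and mean figures, where it is too high (minor)

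*SAP*

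**What the plan says.** The rule in SAP 3.3.6 is: "Early discontinuation visits will be mapped to the chronologically closest not-performed visit". Scheduled visits are taken as recorded in the case report form. The section gives no maximum distance, no analysis window and no exception for PK.

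In Protocol section 1.3, the row "Serum sample for AZD7442 PK assessment" is marked at Visits 2 to 6 and at the early-discontinuation visit, in Table 2 (neonates) and Table 3 (all others). After the first two weeks the nominal PK days are 31, 92, 183 and 366, with windows of +5, ±5, ±10 and ±15 days.

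SAP 4.2.1.1 states that "the serum concentrations for each scheduled time point will be summarized based on the PKS". SAP 4.2.1.2 adds geometric-mean figures, in which "serum concentration-time data will be presented by cohort, route of administration and weight categories". The combined individual plots use actual times, and the concentration listing prints actual times and deviations from schedule.

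Unscheduled visits are treated differently. SAP 3.3.7.1 keeps them out of by-visit summaries, and SAP 3.3.7.2 has its own PK sentence for them: "PK analysis will include the unscheduled concentrations". Early-discontinuation samples have no such sentence.

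**The concern.** Serum concentration at specified time points is a primary endpoint, and the Day 183 and Day 366 rows show how long exposure lasts. Protocol 4.3 says the prophylaxis doses were chosen so that predicted concentrations match the adult range at 6 months; Day 183 is the observed counterpart of that prediction.

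The gaps between late visits are 91 days (92 to 183) and 183 days (183 to 366). Someone who attended every PK visit and then leaves will usually have the next visit as the nearest one not performed. A falling concentration is then reported at a day when it would have been lower. Cells are likely to be small: SAP section 2 puts the full analysis set at 46, split by cohort, route and weight category, so one value can move a mean visibly.

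**Working it through.** **Half-life.** Protocol 4.2.1 equates follow-up to Day 366 with approximately 4 half-lives, so h = 366/4 = 91.5 days. As a check, the amendment summary's previous 456 days for about 5 half-lives gives 91.2 days, and 365/91.2 = 4.00. The documents give no spread; 60 to 120 days is an assumption.

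**Where the rule sends the sample**, with visits held on nominal days:
- Leaves Day 100 after Visit 4: Day 183 is 83 days away and Day 366 is 266 days away.
- Leaves Day 200 after Visit 5: Day 366 is 166 days away.
- Visit 2A (Day 8) has no PK sample, and its only procedure is for Cohorts 2 and 3. If it counts as not performed in Cohort 1, it is 92 days from Day 100 and 192 days from Day 200. Both leavers still map forward.

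**Overstatement of one value**, assuming mono-exponential decline after the peak: ratio = 2^(shift/h).

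| Case | Shift (days) | h = 91.5 | h = 120 | h = 60 |
|---|---|---|---|---|
| Day 100 to Day 183 | 83 | 1.88 | 1.62 | 2.61 |
| Day 200 to Day 366 | 166 | 3.52 | 2.61 | 6.81 |

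**Effect of one Day 200 leaver on the Day 366 geometric mean** of n values (leaver included): factor = 2^(166/(h × n)).

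| n (assumed) | h = 91.5 | h = 120 to h = 60 |
|---|---|---|
| 3 | 1.52 | 1.38 to 1.90 |
| 4 | 1.37 | 1.27 to 1.62 |
| 6 | 1.23 | 1.17 to 1.38 |
| 12 | 1.11 | 1.08 to 1.17 |

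For scale, 46 participants over 2 cohorts × 2 routes average 11.5 per cell before the weight split; actual cell sizes are not given.

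**Smallest cell that shows a mean.** The SAP has two rules. The general one in 3.3.1 reads "Descriptive statistics will only be presented if" n > 3, and cuts n = 3 to median, minimum and maximum. The PK-specific one in 4.2.1.6 needs only three observations above the quantification limit. The floor is therefore 3 under the specific rule and 4 under the general one.

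**Backward case.** If Day 92 was missed and the participant leaves on Day 130, Day 92 is 38 days away and Day 183 is 53. The value goes back to Day 92 and is 1 − 2^(−38/91.5) = 25% too low.

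**With a window limit**, the largest early-sample overstatement is 2^(5/91.5) = 1.04 at Day 92, 2^(10/91.5) = 1.08 at Day 183 and 2^(15/91.5) = 1.12 at Day 366.

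**The case against.** The strongest reply is that safeguards exist and little is exposed. SAP 4.1.3.1 counts among important deviations "Relevant time window deviations expected to influence key safety and/or PK assessments", and these may remove data from the PK set. SAP 4.1.1.1 provides a pre-lock meeting to decide exclusions. The listing would show a 166-day shift plainly. There is no hypothesis test, Protocol 4.2.1 makes population methods the main PK analysis, and Protocol 7.2 expects withdrawal to be uncommon. Most of this stands, and it is why the point is minor. The safeguards are discretionary, however, and neither names early-discontinuation samples. Protocol 7.2 asks for the visit whenever a participant withdraws, so its date need not count as a deviation.

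Three stronger readings are tempting, and the documents do not support them:
- A reader might infer that the primary PK results as a whole are biased. The SAP does not say that mapped times are used in non-compartmental or population analysis, and the listings and combined individual plots use actual times.
- A reader might infer that the error is always upward. A missed earlier visit can send the sample backward, and an IM leaver before Day 31 may still be absorbing.
- A reader might infer still larger shifts for someone leaving just after Visit 5, say on Day 184, or on Day 174 after an early Visit 5. If Visit 2A counts as not performed in Cohort 1, Day 8 is nearer than Day 366 (176 against 182 days; 166 against 192), so these cases map backward and give no dependable figure.

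One step is inferred: the SAP does not state that the mean figures use nominal time, but a mean per time point implies it.

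**Conclusion.** The gap is real. Read literally, SAP 3.3.6 lets a post-peak concentration enter by-visit serum tables and geometric-mean figures at a nominal day months later, overstating that individual's value about 1.9-fold (Day 100 to 183) or 3.5-fold (Day 200 to 366). This rests on a 91.5-day half-life, mono-exponential decline and attendance at the earlier PK visits. The change in a cell mean depends on assumed cell sizes, and the total effect is unknown because leaver numbers are not given. The Cohort 1 Ctrough (182 days post-dose, which is Day 183) is affected only if mapped values feed it, which the SAP leaves open. Severity: minor.

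**What to change.** Add to SAP 3.3.6:

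> For serum PK concentrations, an early-discontinuation sample enters a by-visit summary, a mean figure or an observed Ctrough only if it falls inside the SoA window of a not-performed visit that has a scheduled PK sample. Otherwise it is listed and used at its actual time in NCA and population PK.

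Scheduled visits stay as captured, consistent with Protocol 8.5.2: "Serum samples should still be taken even if the participant is outside the visit window specified in the SoA". Naming visits with a scheduled PK sample also settles the Visit 2A ambiguity for serum PK.

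The cost is one sentence, one programming rule and fewer values in the tables. With earlier visits on nominal days there are 332 possible leaving days from Day 32 to Day 365 (excluding 92 and 183). Only 5 + 10 + 15 = 30 fall inside the next visit's window, so 302 (91%) would leave the by-visit tables. A cell at the display minimum could lose its mean.

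Separate minor correction, unrelated to the mapping: SAP Table 3 sets the treatment Ctrough at 28 days post-dose, and SAP Table 5 lists 28 for this study, but the protocol's sample is Day 31 (+5), which is 30 to 35 days post-dose. At h = 91.5 the sampled value is 1 − 2^(−2/91.5) = 1.5% to 1 − 2^(−7/91.5) = 5.2% below the 28-day value (1.1% to 7.8% over the half-life range). This concerns Cohort 2 only, since Cohort 3 is empty. Define the Cohort 2 Ctrough as the Day 31 visit concentration or a model-predicted 28-day value, and change the Table 5 entry to 30.
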